**Methodology:**

This is a 3-part study:

- Part 1: Single-dose pharmacokinetic assessments of lanthanum carbonate in at least 8 subjects. Part 1 is complete and an interim clinical study report interpreting and summarizing the data is available.
- Part 2a: Open-label, active comparator crossover period. Subjects participating in Part 1 will begin Part 2 immediately following the completion of the pharmacokinetic assessments. Subjects not participating in Part 1 will enter Part 2a. During Part 2a, all subjects will receive calcium carbonate for the first 8 weeks (Treatment Period 1), followed by treatment with lanthanum carbonate for 8 weeks (Treatment Period 2). If needed, there will be a washout period up to 3 weeks between treatment with calcium carbonate (Treatment Period 1) and lanthanum carbonate (Treatment Period 2). No new subjects will be enrolled in Part 2a under Version 6.0 of the protocol.
- Part 2b: Open-label treatment period. Part 2b is modified Part 2a, where subjects will receive treatment with lanthanum carbonate only for 8 weeks. All new subjects will be enrolled in Part 2b only under Version 6.0 of the protocol.
- Part 3: Subjects in Part 2a (including subjects in Treatment Period 1/calcium carbonate treatment arm who discontinued due to hypercalcemia; refer to Section 6.2.1, Dosing, Hypercalcemia) and Part 2b may continue to receive open-label lanthanum carbonate for up to 6 additional months of therapy.

**Screening:**

There will be a 2-week screening period during which eligibility will be determined. Subjects who are eligible to participate will enter a washout period of up to 3 weeks if the phosphorus level is not above KDOQI required levels. During the washout period the existing phosphate binder treatment will be discontinued until phosphate levels have risen above 6.0mg/dL (1.94mmol/L) in subjects aged under 12 years or >5.5mg/dL (1.78mmol/L) in subjects aged over 12 years. At the end of the washout period, subjects will be assessed for inclusion in the study based on their serum phosphorus levels.

**Treatment Period:**

Part 1. At least 8 subjects will undergo pharmacokinetic sampling following a single dose of lanthanum carbonate in order to assess the plasma concentration-time relationship of lanthanum carbonate. At the completion of the pharmacokinetic assessment period, these subjects will enter Part 2 of the study.

Part 2a. Subjects who meet eligibility criteria and who are not participating in Part 1 will be enrolled into Part 2a (Treatment Period 1) and will receive calcium carbonate for the first 8 weeks. At the completion of the first 8 weeks of Part 2a, if required subjects will enter a washout period of up to 3 weeks duration and will then cross over to Part 2a to receive lanthanum carbonate treatment for 8 weeks (Treatment Period 2). No new subjects will be enrolled in Part 2a under Version 6.0 of the protocol.

Part 2b. Subjects who meet eligibility will be enrolled into Part 2b and will receive lanthanum carbonate treatment for 8 weeks. All new subjects will be enrolled in Part 2b only under Version 6.0 of the protocol.

Part 3. At the conclusion of Part 2 (2a and 2b), subjects may continue to receive open-label lanthanum carbonate for up to 6 additional months of therapy (including subjects who participated in Part 2a, Treatment Period 1/calcium carbonate treatment arm, but who discontinued due to hypercalcemia; refer to Section 6.2.1, Dosing, Hypercalcemia).

**Dosing information:**

**Part 1:** Lanthanum carbonate oral powder will be administered in the morning following breakfast on the day after receiving dialysis treatment.

Subjects aged between 10 and 12 years will receive a dose of 500mg lanthanum (as lanthanum carbonate hydrate; SPD405) and subjects aged 12 years and over will receive 1000mg lanthanum (as lanthanum carbonate hydrate; SPD405).

**Part 2a, Treatment Period 1:** Calcium carbonate may be started at the dose taken by the subject prior to starting the study or equivalent. For new subjects dosing will be based on standard clinical practice and the dose will be titrated 2-weekly as appropriate, until the target serum phosphorus level is achieved, or until a maximum daily dose of 6500mg is reached. Once serum phosphorus control is achieved, the dose of calcium carbonate will be maintained until the end of the 8-week calcium carbonate treatment period.

**Part 2a, Treatment Period 2:** At the end of the first 8-week treatment period of Part 2a (ie, Treatment Period 1), all subjects will begin 8 weeks of treatment with lanthanum carbonate following a washout period of 3 weeks, or until phosphorus level is above KDOQI required levels, whichever is sooner. Lanthanum carbonate will be mixed with food and given 3 times a day. If the subject has only 2 meals a day the lanthanum carbonate dose will split equally across the 2 meals with a single dose not exceeding 1000mg. The starting total daily dose of lanthanum carbonate is 1500mg for all subjects. The total daily dose will be titrated 2-weekly, as appropriate, until the target serum phosphorus level is achieved, or until a maximum daily dose of 3000mg is reached. Once serum phosphorus control is achieved or the maximum dose is reached, the dose of lanthanum carbonate will be maintained until the end of the 8-week treatment period. No new subjects will be enrolled in Part 2a under Version 6.0 of the protocol.

**Part 2b:** Subjects will begin 8 weeks of treatment with lanthanum carbonate. Lanthanum carbonate will be mixed with food and given 3 times a day. If the subject has only 2 meals a day the lanthanum carbonate dose will split equally across the 2 meals with a single dose not exceeding 1000mg. The starting total daily dose of lanthanum carbonate is 1500mg for all subjects. The total daily dose will be titrated 2-weekly, as appropriate, until the target serum phosphorus level is achieved, or until a maximum daily dose of 3000mg is reached. Once serum phosphorus control is achieved or the maximum dose is reached, the dose of lanthanum carbonate will be maintained until the end of the 8-week treatment period. All new subjects will be enrolled in Part 2b only under Version 6.0 of the protocol.

**Part 3:** Subjects who complete participation in Part 2 (2a or 2b) may continue to receive lanthanum carbonate for an additional 6 months (including subjects who participated in Part 2a, Treatment Period 1/calcium carbonate treatment arm, but who discontinued due to hypercalcemia). The dosage of lanthanum carbonate will be determined by the Investigator based on serum phosphate levels taken at each study visit up to a maximum dose of 3000mg/day.

**Safety Follow-up:** A safety follow-up telephone call will be made to all subjects or their parent/legally authorized representative (LAR) 7-14 days following the last dose. In the event of early discontinuation due to kidney transplantation, the safety follow-up call will be 30±7 days from the last dose.

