### 6.2 Administration of Investigational Product(s)

#### 6.2.1 Dosing

Both calcium carbonate tablets and lanthanum carbonate powder are to be taken orally.

**Part 1:** Lanthanum carbonate oral powder will be administered in the morning following breakfast at Visit 1.1, which is the day after dialysis treatment.

Subjects aged between 10-12 years will receive a single dose of 500mg lanthanum (as lanthanum carbonate hydrate; SPD405) and subjects aged >12 years will receive a single 1000mg dose of lanthanum (as lanthanum carbonate hydrate; SPD405).

**Part 2a, Treatment Period 1:** Calcium carbonate may be started at the dose taken by the subject prior to starting the study or equivalent. For new subjects, dosing will be based on standard clinical practice. The total daily dose may be adjusted as appropriate, until the target serum phosphorus level is achieved or until a maximum daily dose of 6500mg is reached. Once serum phosphorus control is achieved, the dose of calcium carbonate will be maintained until the end of the 8-week calcium carbonate treatment period.

Investigational product will be dispensed at Visit 2.0 if eligible, however if a washout is required then investigational product will be dispensed at visit W1.

**Part 2a, Treatment Period 2:** At the end of the first 8-week treatment period of Part 2a, all subjects will begin 8 weeks of treatment with lanthanum carbonate following a washout period of up to 3 weeks if necessary (see Section 7.1.2.4). Subjects reaching a level of phosphorus equal to or greater than the age-appropriate KDOQI guidance (aged under 12 years: serum phosphorus >6.0mg/dL [1.94mmol/L] and aged 12 years and older: serum phosphorus >5.5mg/dL [1.78mmol/L]) will be withdrawn from washout and commence treatment with lanthanum carbonate.

Lanthanum carbonate will be started at a total daily dose of 1500mg mixed into meals for all subjects. Lanthanum carbonate will be mixed with food and given 3 times a day. If the subject has only 2 meals a day the lanthanum carbonate dose will split equally across the 2 meals with a single dose not exceeding 1000mg. The total daily dose will be titrated as appropriate, until the target serum phosphorus level is achieved in accordance with KDOQI age guidelines or until a maximum daily dose of 3000mg is reached. Once serum phosphorus control is achieved, the dose of lanthanum carbonate will be maintained until the end of the 8-week lanthanum carbonate treatment period.

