### **7.1.2 Treatment Period**

#### **7.1.2.1 Part 1: Visit 1.1/ Week -5 to -1 ( $\pm 3$ Days)**

Visit 1.1 should be scheduled on the day after dialysis. See [Table 2](#) for a detailed schedule of assessments for this visit.

- Subjects aged between 10 and 12 years will receive a single dose of 500mg lanthanum (as lanthanum carbonate hydrate) and subjects aged 12 years and over will receive a single 1000mg dose lanthanum (as lanthanum carbonate hydrate; SPD405).
- Blood samples for pharmacokinetic analyses will be taken pre-dose and at 3, 5, 6, 8, 12, 24, and 48 hours after dosing.
- Vital signs (blood pressure and pulse) will be recorded pre-dose, and at 24 and 48 hours after dosing.
- A physical examination will be done at 48 hours post-dose.
- Adverse events and changes to concomitant medication will be recorded.

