### 12.3 Statistical Analysis of Pharmacokinetic Data

All of the PK analyses for Part 1 will be performed using the Pharmacokinetic Set 1. All of the PK analyses for Parts 2 and 3 will be performed using the Pharmacokinetic Set 2.

Summary statistics (number of observations, mean, standard deviation, coefficient of variation, median, maximum, minimum, and geometric mean) will be determined for all pharmacokinetic parameters by age group for Part 1. Plasma concentrations at each nominal sampling time will also be summarized by age group for Part 1 using descriptive statistics (number of observations, mean, standard deviation, coefficient of variation, median, maximum, and minimum).

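### The protocol sections disagree on the Part 1 dose for a 12-year-old, and the SAP summarises Part 1 pharmacokinetics by age group, which does not reliably identify dose

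*Protocol*

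**What the plan says.** The Part 1 single dose is set out in three places in the protocol.

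- **Study Synopsis, Dosing information.** "Subjects aged between 10 and 12 years will receive a dose of 500mg lanthanum", and "subjects aged 12 years and over will receive 1000mg lanthanum (as lanthanum carbonate hydrate; SPD405".
- **Section 6.2.1, Dosing.** "Subjects aged between 10-12 years will receive a single dose of 500mg lanthanum", and "subjects aged >12 years will receive a single 1000mg dose of lanthanum".
- **Section 7.1.2.1, Visit 1.1.** "Subjects aged between 10 and 12 years will receive a single dose of 500mg lanthanum". Its upper band starts at 12 years, as in the synopsis.

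SAP Section 12.3 states that summary statistics "will be determined for all pharmacokinetic parameters by age group for Part 1". It treats plasma concentrations at each nominal time in the same way. It states no split by dose and does not define its age groups. The SAP's other by-age tables, including the demographics for Pharmacokinetic Set 1 in Section 7, use 10 to <12 and 12 to <18 years. Section 17 confirms that cut for the by-age tables of disposition, demographics and adverse events.

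Under SAP Section 8.1, Part 1 drug exposure is listed and not summarised. Listing 5.1.1 carries the dose per administration.

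**The concern.** A by-age summary of exposure after a single dose is easy to read only if every subject in an age group had the same dose. The protocol's dose bands and the SAP's age groups both turn on age 12, and the protocol is not consistent about which side of the line a 12-year-old falls on. A child of that age dosed under Section 6.2.1 would be placed by the SAP's usual cut among subjects on the other dose.

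At stake is the meaning of the adolescent Cmax, AUC and concentration rows. Protocol Section 3.1 says that the study data will be evaluated against historical adult exposure. The one adult reference quoted, in the sample-size text, is a 1000mg single dose. A mean over two unlabelled doses is not a clean figure to set beside such a reference.

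**Working it through.** **1. The dose text side by side, for a subject aged 12 in completed years**

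| Source | 500mg band | 1000mg band | Dose at age 12 |
|---|---|---|---|
| Synopsis | between 10 and 12 | 12 and over | 1000mg; also 500mg if the lower band includes 12 |
| Section 7.1.2.1 | between 10 and 12 | 12 and over | same as the synopsis |
| Section 6.2.1 | 10-12 | strictly over 12 | 500mg if the band includes 12, otherwise none assigned |

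Treating 12 as excluded from the lower band removes the overlap in the first two rows, but the third row still never gives a 12-year-old 1000mg. If age is taken exactly, a child of 12 years and one day is over 12 in all three places, and only the 12th birthday is in conflict. The dosing text does not say which kind of age applies.

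**2. Where the SAP puts that subject**

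With groups of 10 to <12 and 12 to <18, every 12-year-old is in the upper group whichever dose was given. Among the parameters in SAP Section 12.2.3, CL/F and Vz/F are computed from the dose, so they already account for it. Cmax, the AUC measures and the concentrations do not.

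**3. The plan's own Part 1 figure**

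Protocol Section 9.13 gives n = 8, SDs of 2.888 (AUC0-t) and 0.177 (Cmax), and 80% assurance of 95% half-widths no wider than 2.86 and 0.18.

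Half-width = t(0.975, 7) × SD/√8 × √(χ²(0.80, 7)/7)

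- AUC0-t: 2.414 before the assurance factor, 2.857 after it (stated 2.86).
- Cmax: 0.148 before, 0.175 after (stated 0.18).

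Both reproduce. They rest on a single 1000mg dose and are not disputed.

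**4. Size of a mixed-dose effect (illustration)**

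Two inputs are not in the documents: the number k of 500mg subjects in a 12 to <18 group of size n, and the ratio r of exposure at 500mg to exposure at 1000mg.

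Proportional fall in the group mean = k(1 − r)/n

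| r | k = 1, n = 8 | k = 1, n = 6 |
|---|---|---|
| 0.5 (dose-proportional) | 0.5/8 = 6.3% | 0.5/6 = 8.3% |
| 0.75 | 0.25/8 = 3.1% | 0.25/6 = 4.2% |
| 1.0 | 0% | 0% |

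For the planning AUC0-t mean of 3.099 ng.hr/mL, r = 0.5 with one subject in 8 gives 2.905.

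**5. Spread**

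Take r = 0.5 and one subject in 8, with that subject's distribution having half the mean and half the SD. The AUC SD goes from 2.888 to 2.797 and the Cmax SD from 0.177 to 0.1755, so both fall slightly. The coefficient of variation rises: AUC from 2.888/3.099 = 93% to 2.797/2.905 = 96%, and Cmax from 0.177/0.296 = 60% to 0.1755/0.2775 = 63%.

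**The case against.** The case for leaving this alone has several parts.

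- **Part 1 is finished.** Both documents say so, and an interim report exists. Rewording the protocol cannot change a dose already given. This stands; the remaining use of the point is in how the SAP presents the results.
- **These sentences may not have governed the dosing.** Protocol Appendix 1 shows that the global age range ran from 6 months to <18 years until Amendment 3.0 of 17 April 2014. The documents do not date the Part 1 dosing. This stands, and it is a further reason to report the dose received and not infer it from age.
- **Mixing would be visible.** Listing 5.1.1 shows each dose, CL/F and Vz/F use it, and the Part 1 data also enter the population model. True, but a reader of the Section 12.3 tables sees none of this in the Cmax, AUC and concentration rows.
- **The age cut is borrowed.** Section 12.3 does not define its groups. This stands as a condition on the point, although Pharmacokinetic Set 1 demographics use the cut at 12.
- **The shift is small against sampling error.** On the planning figures with n = 8, the standard error is 2.888/√8 = 1.021, or 33% of the AUC mean. For Cmax it is 0.0626, or 21% of the mean. This also stands, and it keeps the point minor.

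A reader might infer that adolescent exposure at 1000mg will be understated against adults. The documents do not support that. SAP Section 2.1 puts the adult comparison in a separate document, whose dose and summary measure are not stated, and Section 12.3 does not label any group as 1000mg.

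**Conclusion.** The contradiction is in the current protocol text, and the SAP summary does not guard against it. As written, age group does not reliably identify the Part 1 dose. The point rests on three conditions: age in completed years, a cut at 12 in SAP Section 12.3, and exposure that differs between 500mg and 1000mg. If all hold and one 500mg subject is among 6 to 8, the group mean is lower by about 3% to 8% over ratios of 0.75 to 0.5. If exposure does not differ by dose, the effect is nil.

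Three stronger readings go beyond the documents.

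- **That mixing occurred.** Nothing shows that any 12-year-old received 500mg.
- **That mixing is likely.** With ages assumed uniform over 10 to 17, the chance of at least one 12-year-old is 1 − (7/8)^8 = 66% for 8 subjects, or 1 − (7/8)^10 = 74% for the 10 that the SAP mentions. That is the chance of enrolling a child of that age, not of giving 500mg, and the age assumption is itself unsupported.
- **That the SD would widen.** Under dose proportionality it narrows slightly; only the coefficient of variation rises.

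This is a free improvement to the SAP summary, prompted by a contradiction in the protocol. It is minor.

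**What to change.** In SAP Section 12.3, summarise the Part 1 parameters and concentrations by dose actually received (500mg, 1000mg), or by age group within dose, and state the age groups used. In any comparison with adult exposure data, match on dose.

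Reconcile the Part 1 dosing text in the synopsis, Section 6.2.1 and Section 7.1.2.1, and say whether age is exact or in completed years. This review takes no view on which dose is right. With Part 1 complete, the reconciliation corrects the record only.

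The cost is a sentence in the SAP and a change of column variable. No new data are needed, because the dose is already in Listing 5.1.1. If the 12 to <18 group turns out to have had a single dose, the revised table shows that.

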**Inclusion and exclusion criteria:**

**Inclusion Criteria:**

1. Aged 10 years to <18 years of age at the time of consent.
2. Subject or parent/LAR understand and are able, willing, and likely to fully comply with the study procedures and restrictions defined in this protocol.
3. Male, or non-pregnant, non-lactating female who agrees to comply with any applicable contraceptive requirements of the protocol.
4. Established CKD, on dialysis, and requires treatment for hyperphosphatemia with a phosphate binder.
5. Serum phosphorus levels after a washout period of up to 3 weeks as follows:
  - Age <12 years: Serum phosphorus >6.0mg/dL (1.94mmol/L)
  - Age 12 years and older: Serum phosphorus >5.5mg/dL (1.78mmol/L)
6. Ability to provide written, signed, and dated (personally or via an LAR) informed consent/and assent, as applicable, to participate in the study.

**Exclusion Criteria:**

Subjects are excluded from the study if any of the following criteria are met.

1. Current or recurrent disease (eg, cardiovascular, liver, unstable and uncontrolled gastrointestinal, malignancy, or other conditions) other than CKD or end-stage renal disease that could affect the action, absorption or disposition of the investigational product, or clinical or laboratory assessments.
2. Current or relevant history of physical or psychiatric illness, any medical disorder (except for CKD or end-stage renal disease and related co-morbidities) that may require treatment or make the subject unlikely to fully complete the study, or any condition that presents undue risk from the investigational product or procedures.
3. Unable to eat semi-solid foods or on Total Enteral Alimentation.
4. Known or suspected intolerance or hypersensitivity to the investigational product(s), closely related compounds, or any of the stated ingredients.
5. History of alcohol or other substance abuse within the last year.
6. Current use of any medication (including over-the-counter, herbal, or homeopathic preparations) that could affect (improve or worsen) the condition being studied, or could affect the action, absorption, or disposition of the investigational product(s), or clinical or laboratory assessment.
7. Weight and age of subject are outside of local applicable criteria for blood sample volume limits.
8. Use of another investigational product within 30 days prior to receiving the first dose of investigational product.

**Maximum duration of subject involvement in the study:**

- Planned duration of screening period: Up to 2 weeks if washout not required, otherwise up to 5 weeks
- Planned duration of enrollment period: 64 months
- Planned duration of treatment period: Part 1 - 48 hours, Part 2a - 16 weeks (+ up to 3 weeks for washout between treatments) or Part 2b - 8 weeks, Part 3 - up to 6 months
- Planned duration of follow-up: 7-14 days or  $30 \pm 7$  days in case of kidney transplantation

**Endpoints and statistical analysis:**

**Primary Efficacy Measure:**

- The percentage of subjects achieving age-specific KDOQI targets for serum phosphate level following 8-weeks of treatment with lanthanum carbonate will be descriptively summarized. The KDOQI serum phosphorus targets are defined as:
  - Adolescents aged  $\geq 12$ -<18 years:  $\leq 5.5$ mg/dL (1.78mmol/L)
  - Children aged 10 years -<12 years:  $\leq 6.0$ mg/dL (1.94mmol/L)

**Secondary Measures:**

- The percentage of subjects with serum phosphorus levels below the age-specific KDOQI targets following 8 weeks of treatment with calcium carbonate followed by 8 weeks of treatment with lanthanum carbonate, will be descriptively summarized. The KDOQI serum phosphorus targets are defined as:
  - Adolescents aged  $\geq 12$ -<18 years:  $\leq 5.5$ mg/dL (1.78mmol/L)
  - Children aged 10 years -<12 years:  $\leq 6.0$ mg/dL (1.94mmol/L)
- Changes from baseline in serum phosphorus, calcium and calcium-phosphorus product in hyperphosphatemic children and adolescents with CKD who are on dialysis, following treatment with

lanthanum carbonate for 8 weeks.

- Changes from baseline in serum phosphorus, calcium and calcium-phosphorus product in hyperphosphatemic children and adolescents with CKD who are on dialysis, following treatment with calcium carbonate for 8 weeks and lanthanum carbonate for 8 weeks.
- Change from baseline in serum phosphorus, calcium and calcium-phosphorus product levels at the last visit of each 8-week treatment period during Part 2 and monthly during the 6-month extension phase (Part 3).
- Biochemical bone markers: bone ALP, osteocalcin, TRAP, FGF-23, PTH, sclerostin and fetuin-A before and after each treatment period in Part 2, and at the end of Part 3.
- Height and weight at:
  - Visits 2.0, 2.4, 2.8, and 3.5 (Parts 2a and 3)
  - Visits 1.0, 2.4, and 3.5 (Parts 2b and 3).

